2.9.1 Data handling principles

Zero concentrations will not be included in the geometric mean calculation. Since Tmax is generally evaluated by a nonparametric method, median values and ranges will be given for this parameter.

Missing concentration values will be reported as is in data listings. Concentration values below Lower limit of quantitation will be handled as zero in summary statistics, and reported as is in data listings. Any missing pharmacokinetic parameter data will not be imputed.

2.9.2 Immunogenicity

The presence and/ titer of anti-PDR001 antibodies, at each scheduled time point, will be listed by patients. Overall immunogenicity may be summarized when sample size is sufficient.

2.9.2.1 Sample ADA Status

Each IG sample is assessed in a three tiered anti-drug anti-body (ADA) testing approach. All IG samples are analyzed in the initial screening assay (first tier). Samples testing negative in the screening assay are not subject to a confirmatory assay. Samples testing positive in the screening assay are then subjected to the confirmatory assay to demonstrate that ADA are specific for the therapeutic protein product (second tier). The titer of confirmatory positive samples will be subsequently determined in the titration assay (third tier). Samples identified as

positive in the confirmatory assay are considered ADA positive. Samples can test negative in either the screening or confirmatory assay but for analysis purposes they are not differentiated. The following properties of each sample will be provided in the source data:

- Result of assay according to pre-specified confirmatory cut point: ADA positive (yes) or ADA negative (no)
- Titer (for positive samples): numerical representation of the magnitude of ADA response
- Drug tolerance level: highest drug concentration that does not interfere in the ADA detection method
- Fold titer change (i.e. x-fold): threshold for determining treatment boosted

Sample ADA status is determined based on the following definitions:

- ADA-inconclusive sample: Sample where assay is ADA negative and PDR001 PK concentration at the time of IG sample collection is greater than or equal to the drug tolerance level or missing.
- Unevaluable sample: Sample where assay is not available.
- Determinant sample: Sample that is neither ADA-inconclusive nor unevaluable.

The following definitions apply only to determinant samples:

- ADA-negative sample: Determinant sample where assay is ADA negative and PDR001 PK concentration at the time of IG sample collection is less than the drug tolerance level.
- ADA-positive sample: Determinant sample where assay is ADA positive.

The following definitions apply only to post-baseline ADA-positive samples with a corresponding determinant baseline sample. To be classified as treatment-boosted or treatment-unaffected, both the post-baseline and baseline titer must be non-missing:

- treatment-induced ADA-positive sample: ADA-positive sample post-baseline with ADA-negative sample at baseline.
- treatment-boosted ADA-positive sample: ADA-positive sample post-baseline with titer that is at least *the fold titer change* greater than the ADA-positive baseline titer.
- treatment-unaffected ADA-positive sample: ADA-positive sample post-baseline with titer that is less than *the fold titer change* greater than the ADA-positive baseline titer.

NOTE: PK concentrations which are flagged for exclusion will still be used to determine ADA-inconclusive and ADA-negative samples.

The following summaries of ADA sample status (n and %) will be provided using Immunogenicity prevalence set:

- ADA-positive samples (i.e. ADA prevalence), both overall and by time point (including baseline). For summaries by time point, the denominator is the number of subjects at that time point with a determinant sample.

Listings will be provided of sample ADA status (including titer for positive samples).

2.9.2.2 Subject ADA status

Any IG sample collected after 150 days of the last dose of PDR001 will not be used for summaries or derivations and will only be included in the listing.

Subject ADA status is defined as follows:

- Treatment-induced ADA-positive subject: subject with ADA-negative sample at baseline and at least one treatment-induced ADA-positive sample.
- Treatment-boosted ADA-positive subject: subject with ADA-positive sample at baseline and at least one treatment-boosted ADA-positive sample.
- Treatment-unaffected ADA-positive subject: subject with ADA-positive sample at baseline, no treatment-boosted ADA-positive samples, and at least one treatment-unaffected ADA-positive sample.
- Treatment-reduced ADA-positive subject: subject with ADA-positive sample at baseline and at least one post baseline determinant sample, all of which are ADA-negative samples.
- ADA-negative subject: subject with ADA-negative sample at baseline and at least one post baseline determinant sample, all of which are ADA-negative samples.
- Inconclusive subject: subject who does not qualify as treatment-induced ADA-positive, treatment-boosted ADA-positive, treatment-unaffected ADA-positive, treatment-reduced ADA-positive, or ADA-negative.

The following summaries of ADA subject status (n and %) will be provided using Immunogenicity incidence set:

- Treatment-boosted ADA-positive subjects; denominator is the number of subjects with ADA-positive sample at baseline.
- Treatment-induced ADA-positive subjects; denominator is the number of subjects with ADA-negative sample at baseline.
- ADA-negative subjects: denominator is the number of subjects in Immunogenicity incidence set.
- ADA-positive subjects (i.e. ADA incidence): calculated as the number of treatment-boosted ADA-positive and treatment-induced ADA-positive subjects; denominator is the number of subjects in Immunogenicity incidence set.

Listings will be provided of subject ADA status.

2.10 Biomarkers

2.10.1 Introduction

As a project standard only biomarkers collected in the clinical database will be analyzed.

There may be circumstances when a decision is made to stop sample collection, or not perform or discontinue the analysis of blood / archival tumor samples / fresh tumor biopsies / fine needle aspirates due to either practical or strategic reasons (e.g. issues related to the quality and/or quantity of the samples or issues related to the assay). Under such circumstances, the number of samples may be inadequate to perform a rigorous data analysis and the available data will only be listed and potentially summarized.

2.10.2 Outline of the data analysis

Additional analyses that may be performed after the completion of the final (end-of-study) CSR will be documented in separate reports. These analyses may include but are not limited to the meta-analysis of data from this study combined with data from other studies or the analysis of biomarkers generated from samples collected during the study but analyzed after the database lock and completion of the CSR. The data analysis will be described in an addendum of the SAP or in a stand-alone analysis plan document, as appropriate.

2.10.3 Biomarker objectives

The biomarker objectives and corresponding endpoints are described in [Table 1-1](#).

2.10.4 Biomarker analysis data

The Full Analysis Set will be used for all biomarker analysis. All statistical analyses of biomarker data will be performed on patients treated with PDR001 with biomarker data. [Table 2-9](#) listed the biomarker, collection time and purpose of analysis.

Table 2-9 Sample biomarker summary table

Biomarker	Timepoint	Sample	Purpose of analysis
Immune-related genes, including but not limited to PD-L1, CD8, LAG-3, and TIM-3	Screening/Baseline	Newly obtained or archival tumor sample	Assess potential predictive markers of efficacy of PDR001
Immune-related genes, including but not limited to PD-L1, CD8, and TIM-3	Anytime between C3D1 and End of Treatment	Newly obtained tumor sample	Assess the pharmacodynamic effect of PDR001 in tumor sample
Cytokine analysis markers, including but not limited to IFN- γ , TNF- α , IL-6	C1D1 (pre-dose) C1D8 C1D15 C2D1 (pre-dose) C2D8 C2D15 End of Treatment	Blood sample for plasma cytokine analysis	Assess the pharmacodynamic effect of PDR001 in peripheral blood

Biomarker	Timepoint	Sample	Purpose of analysis

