### 7.1.1 Screening/baseline period

The study IRC/IEC informed consent form must be signed and dated before any screening/baseline procedures are performed, except for evaluations performed as part of standard of care.

Patients will be evaluated against study inclusion and exclusion criteria and safety assessments. For details of assessments, refer to [Table 7-1](#), [Table 7-2](#) and [Table 7-3](#). Screening/Baseline assessments must be repeated if performed outside of the specified screening window ([Section 7.1](#)). The screening failure reason will be entered on the Screening Phase Disposition eCRF.

Submission of a newly obtained tumor sample (formalin fixed, in ethanol) or an archival tumor sample (should a newly obtained tumor sample not be possible for medical reasons) are requested and will be collected, whenever possible, from all patients at screening/baseline. For details refer to [Section 7.2.4](#).

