**Table 7-9 Biomarker sample collection plan**

Sample Type	Visit/ Time point	Slides/Volume	Marker*	Purpose
Tumor samples				
Newly obtained tumor sample or archival tumor block (if newly obtained tumor sample is not feasible) (all patients)	Screening/Baseline	Newly obtained formalin fixed tumor sample in ethanol (3-6 passes) or archival FFPE tumor block or a minimum of 15 freshly cut slides from archival paraffin tumor tissue	RNA expression of immune-related genes IHC expression of markers such as: PD-L1 LAG-3 TIM-3 CD8, Foxp3 TIL counts Protein expression of immune-related markers	Assess expression status of potential predictors of efficacy Pharmacodynamic markers (Baseline)
Newly obtained tumor sample (patients in PDR001 arm)	Any time between C3D1 and End of Treatment	Newly obtained formalin fixed tumor sample in ethanol (3-6 passes)	RNA expression of immune-related genes PD-L1, CD8, Foxp3 TIL counts Protein expression of immune-related markers	Pharmacodynamic effect (on-treatment)
Blood samples				
Blood sample for plasma cytokine analysis (patients in PDR001 arm)	C1D1 (pre-dose) C1D8 C1D15 C2D1 (pre-dose) C2D8 C2D15 End of Treatment	Approximately 5 mL	Cytokine analysis (e.g., IFN- $\gamma$ , TNF- $\alpha$ , IL-6)	Pharmacodynamic effect (on-treatment)

Note: On days and time points when biomarker and pharmacokinetic blood samples are being collected, the PK sample must be drawn first (patients in PDR001 arm).

\*Markers are listed according to level of priority.

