1.2 Study objectives and endpoints

Objectives and related endpoints are described in [Table 1-1](#) below.

Table 1-1 Objectives and related endpoints

Objective	Endpoint	Analysis
Primary		
To assess the efficacy of PDR001 versus investigator's choice of chemotherapy in patients with moderately differentiated/undifferentiated locally advanced recurrent or metastatic NPC who progressed on or after first-line therapy	Progression free survival (PFS) as per RECIST v1.1 using central assessment	Section 2.6
Secondary		
To evaluate the anti-tumor activity of PDR001 versus investigator's choice of chemotherapy in patients with moderately differentiated/undifferentiated locally advanced recurrent or metastatic NPC who progressed on or after first-line therapy	Overall survival (OS), overall response rate (ORR), duration of response (DOR), time to progression (TTP) and immune related progression free survival (irPFS) as per irRC using central assessment	Section 2.7
To characterize the safety and tolerability of PDR001	Safety: Incidence and severity of adverse events (AEs) and serious adverse events (SAEs), including changes in laboratory parameters, vital signs and electrocardiograms (ECGs)	Section 2.8

Objective	Endpoint	Analysis
To characterize the pharmacokinetic profile of PDR001 (patients in PDR001 arm)	Serum PK parameters (e.g. AUC, Cmax, Tmax, half-life); Serum concentration vs. time profiles	Section 2.9
To assess emergence of anti-PDR001 antibodies following one or more intravenous (i.v.) infusions of PDR001 (patients in PDR001 arm)	Presence and/or concentration of anti-PDR001 antibodies	Section 2.10
To assess potential predictive markers of efficacy of PDR001 in tumor sample (patients in PDR001 arm)	Assess potential associations between expression of PD-L1, CD8, Foxp3 and other immunological markers such as Lymphocyte activation gene-3 (LAG-3), T-cell immunoglobulin domain and mucin domain-3 (TIM-3), with anti-tumor activity	Section 2.10
To assess the pharmacodynamic effect of PDR001 in tumor sample (patients in PDR001 arm)	TIL counts and expression of immune-related genes (RNA/protein in tumor sample)	Section 2.10
To assess the pharmacodynamic effect of PDR001 in peripheral blood (patients in PDR001 arm)	Assess peripheral, soluble ligands and cytokine levels (including but not limited to IFN- γ , TNF- α , IL-6)	Section 2.10

2 Statistical Methods

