2.10.5 Data analysis of biomarkers

Basic analysis and reporting are specified in [Table 2-10](#).

Percent change is calculated as $((\text{visit } i - \text{baseline})/\text{baseline}) * 100$.

Fold change is calculated as $\text{visit } i / \text{baseline}$.

Table 2-10 Reporting of analysis

Biomarker	Report
Immune-related genes, including PD-L1, CD8, LAG-3 and TIM-3 from tumor sample	Listing of biomarkers, including demographic variables, collect time point, levels and clinical endpoints.
	Summary table: levels at each time point (baseline and post-baseline) and change/percent change/fold change from baseline at each time point. Descriptive statistics include N, mean, standard deviation, % CV, median, minimum and maximum. For fold change, geometric mean and geometric % CV will also be included.
	Summary tables: PFS will be summarized for subjects with a. PD-L1 high (PD-L1 $\geq 50\%$)/mid (PD-L1 1% - 50%)/low (PD-L1 $< 1\%$) expression at baseline and b. CD8 $< 1\%$ CD8 $\geq 1\%$ expression at baseline using the Kaplan-Meier (KM) method. Median PFS, with corresponding 90 CI, and 25 th and 75 th percentiles (Brookmeyer and Crowley 1982 , Klein and Moeschberger 1997) will be presented. KM estimates for PFS proportions at specific timepoints, along with 95% CI (Greenwood's formula , Kalbfleisch and Prentice 2002) will also be provided.
Cytokine analysis markers, including but not limited to IFN- γ , TNF- α , IL-6 from blood sample	Summary table: levels at each time point (baseline and post-baseline) and change/percent change/fold change from baseline at each time point. Descriptive statistics include N, mean, standard deviation, % CV, median, minimum and maximum. For fold change, geometric mean and geometric % CV will also be included.
	Listing of biomarkers, including demographic variables, collect time point, levels and clinical endpoints.

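### The potential predictive markers are analysed only in PDR001-treated patients under SAP 2.10.4, which cannot separate prediction from prognosis, and SAP 2.6.2 does not clearly say otherwise

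*SAP*

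**What the plan says.** **Purpose.** SAP Table 1-1 (section 1.2) lists the objective "To assess potential predictive markers of efficacy of PDR001 in tumor sample (patients in PDR001 arm", closing the bracket there. Protocol Table 3-1 carries the same objective with the same limit. The endpoint beside it is an assessment of potential associations between marker expression and anti-tumor activity. SAP Table 2-9 gives the purpose of the baseline tumor markers (PD-L1, CD8, LAG-3, TIM-3 and others) as "Assess potential predictive markers of efficacy of PDR001".

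**Population.** SAP 2.10.4 first states "The Full Analysis Set will be used for all biomarker analysis". Its next sentence is "All statistical analyses of biomarker data will be performed on patients treated with PDR001 with biomarker data". The FAS holds every randomized patient in both arms; the second sentence does not.

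**Samples.** Under Protocol 7.1.1, baseline tumor samples "will be collected, whenever possible, from all patients at screening/baseline". Protocol Table 7-9 also marks the baseline tumor row as applying to all patients.

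**Analysis.** SAP Table 2-10 plans Kaplan-Meier summaries of PFS by three PD-L1 classes and two CD8 classes. No contrast between arms within a marker level is planned, and no arm-by-marker term. SAP 2.6.2, in the paragraph that names the FAS, adds Kaplan-Meier estimates by PD-L1 and CD8 without saying whether they are split by arm. SAP 2.2.3 drops subgroup analyses from the final CSR because the primary result was not statistically significant.

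**Details in Table 2-10.** The interval is given as "Median PFS, with corresponding 90 CI", while the same cell uses 95% for PFS proportions and SAP 2.6.2 uses 95% for the median. A PD-L1 value of exactly 50% meets both the high and the mid definition.

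**The concern.** A marker is predictive if it changes the effect of PDR001 relative to chemotherapy. It is prognostic if it goes with longer or shorter PFS whatever the treatment. Data from PDR001-treated patients alone show the sum of the two effects and cannot divide it.

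This matters here because Protocol 2.1 reports that PD-L1 overexpression went with worse disease-free survival in NPC. Prognosis may therefore be mixed into any PD-L1 result, and it can either mimic or hide a predictive effect. A single-arm split of PFS reported under an objective called predictive could be used to select or reject patients for later studies on evidence that does not bear on that choice.

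**Working it through.** **1. The plan's own figure.** The biomarker section states no sample size or precision, so the check starts from the design in SAP section 3: hazard ratio (HR) 0.55, one-sided alpha 0.10, power 85%, 2:1 allocation, 70 events.

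- Schoenfeld events = (1.2816 + 1.0364)² / [(2/3)(1/3)(ln 0.55)²] = 5.373 / 0.0794 = 67.7, rounded up to 68, against 70 stated.
- Power at 70 events = Φ(√(70 × 0.0794) − 1.2816) = Φ(1.076) = 0.859, against 0.85 stated.

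The design reproduces.

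**2. What PDR001-only data can show.** Write the log hazard as a treatment term + γ × marker + δ × treatment × marker. The marker contrast is γ + δ on PDR001 and γ on chemotherapy. Only the difference between the two gives δ, the predictive part.

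Table 2-10 reports medians, so the same point is shown in medians. Assume exponential PFS, with the design medians (10 and 5.5 months) as the marker-low medians. A marker HR of 0.5 doubles the median.

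| Marker type | PDR001, low / high | Chemotherapy, low / high | Ratio of marker HRs (PDR001 / chemotherapy) |
|---|---|---|---|
| Purely prognostic | 10 / 20 months | 5.5 / 11 months | 0.5 / 0.5 = 1.0 |
| Purely predictive | 10 / 20 months | 5.5 / 5.5 months | 0.5 / 1.0 = 0.5 |

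The PDR001 column is identical in both rows. More patients in that arm would not help.

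The error can also run the other way. If high PD-L1 raised the hazard 1.5-fold on chemotherapy and the true ratio were 0.67, the PDR001 patients would show 1.5 × 0.67 = 1.0, and a predictive marker would be missed.

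**3. Who is left out.** Protocol Amendment 06 (Study status) gives 122 randomized, 82 of them to PDR001. So 122 − 82 = 40 were randomized to chemotherapy, and 40/122 = 33%. This is an upper limit, because crossover patients were also treated with PDR001 and might be counted in.

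**4. What the control arm would add.** SAP section 3 assumes 14 months of uniform accrual, 20 months in total, 15% dropout at 12 months, and 76 + 38 patients. With λ = ln 2 / median and g = −ln(0.85)/12, expected events per arm are n × the average over follow-up t from 6 to 20 months of [λ/(λ+g)] × [1 − exp(−(λ+g)t)]. This gives 40.7 on PDR001 and 27.8 on chemotherapy, 68.5 in all. Scaled to 70, the split is 41.6 and 28.4.

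The standard error (SE) of the log ratio of marker HRs is √(sum of 1/events over the four arm-by-marker cells). The documents give neither the marker-high share nor the evaluable share, so both are assumed over a range.

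| Marker-high | Evaluable | Cell events (PDR001; chemotherapy) | SE | 95% interval factor, exp(1.96 × SE) |
|---|---|---|---|---|
| 50% | 100% | 20.8, 20.8; 14.2, 14.2 | 0.49 | ×/÷ 2.6 |
| 20% | 100% | 8.3, 33.3; 5.7, 22.7 | 0.61 | ×/÷ 3.3 |
| 50% | 60% | 12.5, 12.5; 8.5, 8.5 | 0.63 | ×/÷ 3.4 |
| 20% | 60% | 5.0, 20.0; 3.4, 13.6 | 0.79 | ×/÷ 4.7 |

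For a true ratio of 0.5 at one-sided 0.10, power is Φ(0.693/SE − 1.2816), or 56% in the first row and 34% in the last. The final CSR may hold more than 70 events, which would narrow the intervals. With both arms the ratio can be estimated, but only imprecisely.

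**The case against.** **The restriction belongs to the objective.** Both documents limit the objective to the PDR001 arm, and its endpoint is association with anti-tumor activity. Protocol section 10 speaks only of exploring the PD-L1 correlation. This stands: a reader might infer that the planned analysis fails its own endpoint, and it does not. What it cannot support is the word predictive in the objective and in the Table 2-9 purpose.

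**SAP 2.6.2 may already cover both arms.** A reader might infer that the control arm is definitely excluded. The documents do not settle that, because SAP 2.6.2 and the FAS sentence in 2.10.4 point the other way. Even so, 2.6.2 does not say within arm, gives no interaction estimate, and conflicts with the sentence that governs all biomarker statistics.

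**The control samples may not exist.** It is tempting to say that available control data are being discarded. Protocol inclusion criterion 7 says only that a sample may be submitted, and Protocol 7.2.4 and SAP 2.10.1 allow collection or analysis to be dropped. No count of evaluable control samples is given. This stands, and the fix has to allow for it.

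**Crossover patients.** The words about treatment with PDR001 could be read to bring crossover patients in, with PFS events that occurred on chemotherapy. That is not what the plan says elsewhere: the objective names the PDR001 arm, and SAP 2.1 and 2.1.1 keep crossover as a separate group with its own reference date. SAP 2.10.4 is simply silent on which patients and which start date apply.

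**Low yield after a non-significant primary result.** This is fair. Protocol 2.1 reports 89.5% of 115 tumors with high PD-L1 and CD8. If 10.5% were marker-low (the cut-off may differ from the SAP's), the control arm would have about 28.4 × 0.105 = 3 low-marker events, and the interval would be about ×/÷ 4.7 even with every sample evaluable. Three PD-L1 classes would be sparser. This argues for a descriptive label, not for leaving out the only comparison that addresses prediction.

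**Conclusion.** The concern holds in a limited form. If SAP 2.10.4 is followed as written, the analysis shows how PFS varies with marker level among PDR001-treated patients. That meets the association endpoint but cannot support a statement that a marker is predictive, at any sample size. SAP 2.6.2 and 2.10.4 disagree about the population and need to be reconciled.

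Up to 40 of 122 randomized patients (33%) are affected; the number with control-arm marker data is not stated. A reader might also infer that the plan would report a misleading hazard ratio. It would not: Table 2-10 plans medians, percentiles and PFS proportions, with no hazard ratio or test. The risk lies in how those curves are interpreted.

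The primary PFS result is untouched. The precision range of ×/÷ 2.6 to 4.7 rests on 70 events, the design's event split, 20–50% marker-high and 60–100% evaluable. The 90% interval and the overlap at 50% are separate drafting slips that do not bear on prediction versus prognosis.

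**What to change.** - **Population.** Reconcile SAP 2.6.2 and 2.10.4 so that the baseline PD-L1 and CD8 analyses use all FAS patients with an evaluable baseline tumor result, by randomized arm, with PFS counted from randomization. This also settles the place of crossover patients. On-treatment tumor and cytokine analyses can stay with the PDR001 arm, where those samples are taken.
- **Output.** Give Kaplan-Meier PFS by marker level within each arm, with the number evaluable per arm. Where cell counts allow, add the arm-by-marker ratio of hazard ratios with a 95% interval from a Cox model stratified by disease status.
- **Label.** Call it exploratory and post hoc to the primary result. Record in SAP section 4 that it goes beyond the PDR001-arm objective, and align it with SAP 2.2.3.
- **Fallback.** If too few control samples are evaluable, report association with outcome in PDR001-treated patients and do not call it predictive.
- **Drafting.** Define mid PD-L1 as 1% to <50%, and use 95% for the median as elsewhere.

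The cost is SAP wording, one more model, and estimates that will be imprecise.
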